DFV890 was evaluated in a completed Phase 1 first-in-human (FIH) trial in healthy volunteers (CDFV890A02101), a Phase 2 SARS-CoV-2 (COVID-19) trial (CDFV890D12201) and is being assessed in ongoing Phase 2 clinical trials in familial cold auto-inflammatory syndrome (CDFV890A12201), osteoarthritis (CDFV890B12201), and myelodysplastic syndrome (CDFV890G12201).

MAS825 is a CCI bispecific monoclonal antibody (mAb) against human IL-1 β and human IL-18 derived from CCI (anti-IL-1 β or CCI) and CCI (anti-IL-18) antibodies. MAS825 was evaluated in a completed Phase 1 FIH trial in healthy volunteers (CMAS825A02101), a Phase 2 COVID-19 trial (CMAS825F12201) and is being assessed in ongoing Phase 2 clinical trials in patients with nucleotide-binding oligomerization domain-like receptor family caspase activation and recruitment domain-containing 4 protein (NLRC4) gain-of-function (NLRC4-GoF) mutations (CMAS825D12201) and hidradenitis suppurativa (HS) (platform study CCFZ533H12201BC).

MAS825 can neutralize IL-1 β and IL-18 driven effects regardless of the source of the cytokines, while DFV890 can reduce NLRP3 inflammasome driven production of IL-1 β and IL-18. The relative contribution of the NLRP3 inflammasome to circulating cytokine levels in the CHIP population with known coronary heart disease is unknown. DFV890 tablets are taken orally (daily administration evaluated in this study) and MAS825 solution is injected subcutaneously (CCI), with only a single dose being evaluated in this study). A key marker of response, IL-6 levels, which robustly predicted CVD benefit in the CANTOS trial, will be used as a primary endpoint in this trial. In addition, for DFV890, IL-18 levels will be used a co-primary endpoint to capture the additional potential benefit above and beyond the IL-1 β /IL-6/hsCRP pathway. IL-18 levels cannot be accurately used as an endpoint for MAS825 as the mAb binds to IL-18; although exploratory assays of total IL-18 and downstream markers of IL-18 activation, such as interferon- γ (IFN- γ), CXCL9, and CXCL10 will be incorporated.

Through the inhibition of IL-1 β and IL-18, DFV890 and MAS825 have the potential to significantly reduce cardiovascular risk in patients. The safety profile, pharmacodynamic (PD) effects, and risk-benefit ratio support further studies of DFV890 and MAS825 to reduce inflammatory markers, and eventually MACE, in patients with known coronary heart disease and CHIP.

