2.11 Biomarkers

All participants in the PD analysis set will be included in the biomarker analysis. The following exploratory biomarkers may be analyzed in this trial and reported in the CSR.

- Pharmacodynamic, inflammation-related biomarkers:
 - Inflammatory biomarkers: hsCRP
 - Soluble Biomarkers: soluble ASC, hsIFN- γ , and vWF
- Immunophenotyping: A whole blood monocyte / neutrophil panel will evaluate the total cell count and percentage of monocyte and neutrophil subsets in peripheral blood of patients.
- Target capture biomarkers for MAS825: total IL-1 β , total IL-18 and IL-18bp.
- CVD-related biomarkers
 - Lipid parameters: total cholesterol, HDL-C, triglycerides (TGs), LDL-C, Lp(a), apolipoproteins

For each of the biomarker endpoints, the actual value, the change from baseline, and the percent change from baseline will be listed by treatment sequence, participant, and visit/timepoint. Summary statistics will be provided by treatment/treatment sequence and visit/timepoint for the actual value, the change from baseline and percent change from baseline. The frequency (n, %) of values outside of the limits of quantification will be reported in each table.

The following inflammation-related exploratory biomarkers: hsCRP, soluble ASC, hsIFN γ , vWF, Interleukin-1b (IL-1b), IL-18, IL-18bp and monocyte/neutrophil panel (whole blood) and disease-related biomarkers (LDL, Lp(a), and apolipoproteins) will be analyzed using a linear mixed effects model of the same form as the traditional model previously specified for the primary endpoint. When appropriate, the analysis will be restricted to DFV890 or MAS825 sessions with the corresponding control sessions.

As for the analysis on primary endpoint log transformations will be applied. Immunophenotyping endpoints considering percentages vs total monocytes/neutrophils will be summarized and listed while they won't be analyzed using any statistical model.

Corresponding plots showing the predicted response at each treatment dose (or time for MAS825) with associated 80% CIs will also be produced, together with individual plots by treatment (by time for MAS825 arm).

Handling of LLOQ and ULOQ

Biomarker data are reported as concentration results, measured using a specific assay with a working range defined by the two limits: Lower limit of quantification (LLOQ) and Upper limit

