of quantification (ULOQ). Values which fall below the LLOQ or above the ULOQ are reported as $< \text{LLOQ} * \text{dilution factor}$ (dilution factor: if sample diluted and concentration measured still below LLOQ) and $> \text{ULOQ} * \text{dilution factor}$, respectively.

To ensure that biomarkers only have numerical values, censored values will be imputed as follows:

- Values below the LLOQ are replaced by $\text{LLOQ}/2$.
- Values above the ULOQ are replaced by ULOQ.

Imputed values are used for summary statistics, inferential analyses and plots (with a special symbol). Values below LLOQ and values above ULOQ are shown as such in the listings.

If the proportion of imputed data is more than 20% for any treatment group at any time point, a footnote is added to the summary statistics table stating that the proportion of values outside the limits of quantification is more than 20% for some treatment groups at some time points and that in such cases summary statistics may be heavily biased.

If the proportion of imputed data for a given biomarker, across all treatment groups and time points, is more than 50%, no summary statistics are provided and the data are only listed.

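### The pooled 50% imputation rule in SAP 2.11 could reduce a MAS825 target-capture marker to a listing if most samples taken without MAS825 are below the LLOQ

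*SAP*

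**What the plan says.** The relevant text is in SAP 2.11, mostly under the handling of LLOQ and ULOQ.

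- **Imputation.** "Values below the LLOQ are replaced by" half the LLOQ, and the imputed values feed the summaries, models and plots.
- **Mild rule, judged cell by cell.** "If the proportion of imputed data is more than 20% for any treatment group at any time point, a footnote is added".
- **Severe rule, judged on the pool.** When the imputed share for one biomarker, "across all treatment groups and time points, is more than 50%, no summary statistics are provided and the data are only listed". No marker is exempted. Protocol 9.5.1 gives the same LLOQ/2 imputation but contains no suppression rule.
- **Markers concerned.** Total IL-1β, total IL-18 and IL-18bp are listed as "Target capture biomarkers for MAS825". Their role follows from Protocol 2.2: "IL-18 levels cannot be accurately used as an endpoint for MAS825 as the mAb binds to IL-18".
- **Planned analysis.** IL-1β, IL-18 and IL-18bp are among the markers that "will be analyzed using a linear mixed effects model of the same form as the traditional model previously specified for the primary endpoint", on the log scale. The SAP adds: "When appropriate, the analysis will be restricted to DFV890 or MAS825 sessions with the corresponding control sessions".
- **Who contributes.** SAP 2.11 takes the whole PD analysis set into the biomarker analysis, and Protocol 8.8 has samples drawn from everyone.
- **Count of values outside limits.** SAP 2.11 reports the number and percentage outside the quantification limits, but as part of each summary table.

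**The concern.** The milder consequence (a footnote) is triggered by a single group and visit, while the harsher one (no tables) depends on a pool dominated by participants who never received MAS825. For most biomarkers this matters little. For a target-capture marker, the pattern of interest may be a shift from unquantifiable before dosing to quantifiable after it. In that case the samples without MAS825 could push the pool over 50% and remove the tables for the arm in which the assay worked.

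Read literally, the count of quantifiable values would go too, because it is promised only inside those tables. Listing only also suggests that the mixed model and its plots would be dropped, although the sentence names only summary statistics. What is at stake is the tabulated evidence that MAS825 bound IL-1β, the target that Protocol 8.3.3 places directly upstream of IL-6.

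**Working it through.** **Inputs**

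- Allocation (SAP 3): 28 participants at 4:4:4:1:1, so 28 × 4/14 = 8, 8, 8 and 28 × 1/14 = 2, 2.
- Sequences (SAP 2.1.1.2): sequence 1 is MAS825, and its later data stay assigned to MAS825. Sequences 2 and 3 start on placebo, sequence 4 starts on DFV890, and sequence 5 is placebo throughout.
- Visits: baseline and Days 22, 43, 64, 85 and 92, as in the laboratory time points of SAP 2.7.3. This is an assumption for the target-capture sample, whose row in the assessment schedule is not in the text available to me. Other visit sets are shown below.
- Complete sampling is assumed. *Without MAS825* covers all baselines and all placebo and DFV890 samples.

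**Check against a figure in the plan.** Placebo sessions = 8 (sequence 2) + 8 (sequence 3) + 2 × 4 (sequence 5) = 24, which matches SAP 2.4.1.

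**Formula.** Let u be the fraction below the LLOQ among samples without MAS825, and q the fraction quantifiable among MAS825 post-dose samples. Let U and M be the two sample counts.

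Imputed share = (u × U + (1 − q) × M) / (U + M). With q = 100%, the rule triggers when u > 0.5 × (U + M) / U.

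**All sequences counted, six visits.** Total 28 × 6 = 168; M = 8 × 5 = 40; U = 168 − 40 = 128.

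- Share of the pool without MAS825: 128/168 = 76.2%. This is also the imputed share when u = 100%.
- Break-even: 84/128 = 65.6%.
- Imputed share = u × 128/168, so u = 50% gives 38.1%, 60% gives 45.7%, 70% gives 53.3% and 80% gives 61.0%.
- If a quarter of the MAS825 post-dose values (10 of 40) were also below the LLOQ, the break-even falls to (84 − 10)/128 = 57.8%.

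**Other visit sets and denominators (q = 100%)**

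| Values counted | M | U | Imputed if u = 100% | Break-even u |
|---|---|---|---|---|
| All sequences, baseline + Days 22 to 85 | 32 | 108 | 77.1% | 64.8% |
| All sequences, also screening and Day 92 | 40 | 156 | 79.6% | 62.8% |
| All sequences, Days 22 to 85 only | 32 | 80 | 71.4% | 70.0% |
| MAS825 and placebo sessions to Day 85, with baselines (24 + 8 + 18) | 32 | 50 | 61.0% | 82.0% |
| MAS825 and placebo sessions to Day 85, post-baseline only | 32 | 24 | 42.9% | cannot trigger |
| MAS825 arm only, baseline + Days 22 to 85 | 32 | 8 | 20.0% | cannot trigger |
| MAS825 arm only, also Day 92 | 40 | 8 | 16.7% | cannot trigger |

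The 18 baselines in the fourth row belong to the participants who start on placebo (8 + 8 + 2). The outcome therefore turns on two things that the documents leave open: the below-LLOQ rate without MAS825, and which samples form the denominator.

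**The case against.** The strongest objection is that the trigger is hypothetical. Neither document gives an LLOQ, a baseline level or an expected below-LLOQ rate for total IL-1β. A reader might infer that samples without drug are unquantifiable and post-dose samples quantifiable, so that suppression is to be expected. The documents do not say so, and at or below roughly 63% to 70% below the LLOQ the rule does no harm while the post-dose values are quantifiable. This objection stands, and the point holds only as a conditional.

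Second, sampling everyone does not mean assaying everyone. Protocol 8.7 and 8.9 collect PK and immunogenicity samples from all participants but evaluate MAS825 concentrations and antibodies only in MAS825 recipients. The objectives tables tag total IL-18 as MAS825-only, though they put no such tag on total IL-1β. If the assay is confined to the MAS825 arm, the rule does not trigger. The text does not settle this.

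Third, the analysis may be restricted to MAS825 and control sessions. That sentence concerns the analysis and does not redefine the 50% denominator. If it were read as doing so, the risk would vanish for post-baseline sessions alone, but not once baselines are counted.

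Fourth, a reader might infer that a null IL-6 result could then not be interpreted at all. That goes too far. Individual values are still listed, and with about 8 MAS825 participants a clear shift would be visible there. Total IL-18 and IL-18bp are judged separately under the rule, and MAS825 serum concentrations are a secondary endpoint. None of these replaces a table for IL-1β binding, but they limit the loss.

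Lastly, a cell-by-cell 50% rule for every biomarker is not clearly better. Sequences 4 and 5 have two participants each, so one sample would decide whether a cell is summarised, and contrasts built on LLOQ/2 would be no sounder.

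**Conclusion.** The point holds as a conditional, minor weakness. The rule is pooled as written, and with all sequences and six visits counted, 76% of the pool is without MAS825. Total IL-1β would be reduced to a listing if more than about two thirds of those values were below the LLOQ (62.8% to 70.0% over the visit sets considered), even with every post-dose MAS825 value quantifiable. This rests on assay and counting in all sequences, the assumed visits and complete sampling. Under the narrower denominators shown above the rule does not trigger. The markers are exploratory, so the primary IL-6 and IL-18 conclusions and the sample size are unaffected.

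**What to change.** Amend SAP 2.11 before the assay results are reviewed:

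1. Exempt total IL-1β, total IL-18 and IL-18bp from the pooled 50% suppression.
2. Always tabulate the number and percentage quantifiable by visit for these markers, MAS825 versus placebo. This needs no imputed values.
3. Give full summaries for MAS825 post-dose visits with at most 50% imputed.
4. Do not report change from baseline or model contrasts that rest mainly on LLOQ/2.

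In the extreme case (u and q both 100%), MAS825 post-dose visits would have 0% imputed and be fully summarised, while baseline and placebo would show that no value was quantifiable.

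The cost is a short SAP addition and one table per marker. The small downside is that some cells show only a proportion. The pooled rule can stay as it is for the other biomarkers.

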2.12 Other Exploratory analyses

Exploratory targeted genetic and proteomic analyses, reported in CSR or separated documents, may include but are not limited to:

- Presence of somatic mutations (Clonal Hematopoiesis of Indeterminate Potential (CHIP)) at baseline and EOT.
- Presence of specific gene SNPs (not included in the CSR)
- Longitudinal treatment-induced changes in the circulating proteome (serum or plasma, not included in the CSR)

The presence of CHIP (as assayed by the central laboratory) will be reported in the CSR. More than one somatic mutation may be detected for each participant at each timepoint assayed (Day 1 [baseline] and Day 85 [EOT]) among the mutations assayed on the TSO500 platform. Mutations will be characterized in terms of gene location/allele change, protein location/amino acid change (if any), and cDNA change. VAF values will be multiplied by 100 to be expressed in terms of a percentage. Data will be listed by treatment sequence and participant.

The listing will also include the VAF change from baseline and data collected during the visits not included in the PD analysis set (if any) appropriately flagged. If a mutation is detected at baseline but not at EOT, then no value will be imputed and no change for that participant's mutation VAF will be reported.

Summary statistics of VAF change from baseline by treatment sequence will be provided for TET2 or DNMT3A both at the single mutation and at the gene level. Changes from baseline at the gene level will be summarized firstly deriving an average per participant over the different mutations within the same gene, followed by an average by treatment sequence. This procedure assigns the same weight to all the participants.

In this analysis, only cases with VAF \geq 2% at baseline will be considered and change will be reported across three treatment groups (MAS825 arm [Sequence 1], combined DFV890 arms [Sequence 2-4], and placebo-only arm [Sequence 5]).

2.13 Interim analysis

No interim analysis was originally planned for this study but ad-hoc interim analyses may be conducted to support decision making concerning the current clinical study, Novartis clinical development projects in general or in case of any safety concerns. The clinical team may communicate interim results (e.g., evaluation of Proof of Concept (PoC) criteria or information needed for planning/modifying another study) to relevant Novartis teams for information, consulting and/or decision purposes.

An unblinded ad-hoc interim assessment will be eventually performed considering the results of the first batch of IL6 and IL18 samples. The objectives of this interim assessment are:

- To investigate if the profile of the response is compatible with an Emax model/ the presence of convergence issues related to this model
- An assessment of within and between subjects variability
- An assessment of the power of the study, taking into account the results seen so far

On the basis of the interim results the study team may propose an increase of the sample size in case of results promising but not fully consistent with the original assumption. No reduction of the sample size can be applied, also because the interim will be completed after the completion of the enrollment phase (relative to the planned target). In absence of safety concerns the on-going participants will complete the study as planned.

3 Sample size calculation

Twenty-eight (28) randomized participants in a 4:4:4:1:1 allocation to the treatment sequences will result in, approximately, 8 participants randomized to each of the MAS825-only sequence and the first two ascending dose sequences of DFV890, and 2 participants to the third ascending dose sequence of DFV890 and to the placebo-only sequence.

This allocation of participants will provide at least 80% power of a statistically significant difference from pooled placebo and meeting criteria 1 below if the true, maximum effect of DFV890 on IL-6 and IL-18 within the dose range studied is a 30% reduction (i.e., $\log(0.7) = -0.36$, there is no effect on placebo (i.e., $E_0 = 0$), and the ED₅₀ is 20 mg and the within subject SD is 0.4. The variability was assessed from CANTOS trial of canakinumab using placebo-only data through 24 months. The assumed within subject variability of IL-18 is smaller than IL-6 so the sample size is driven by IL-6. This calculation assumes no correlation between the two markers.

The assumed true E_{max} is approximately -0.5, or $\log(0.6)$, representing a 40% reduction.

From the model-based quantities, the following efficacy criteria will be evaluated at the median baseline value of the biomarker and the median baseline body weight:

1. At least one of the following is observed in relation to placebo at the 100 mg dose:
 - IL-6 reduction \geq 25%, or

- IL-6 reduction $\geq 20\%$ + IL-18 reduction $\geq 10\%$, or
 - IL-6 reduction $\geq 15\%$ + IL-18 reduction $\geq 20\%$.
2. For any of the above criteria that are achieved, the one-sided p-value for the comparison of DFV890 vs. placebo for the associated biomarker(s) is less than 0.1.

Simulations have shown that there is at least 80% power in achieving statistical significance at the 10% level and the mean effect as shown above (with type 1 error of $\leq 10\%$)

This allocation of participants will also provide at least 80% power of showing a statistically significant difference between MAS825 and pooled placebo, if the true effect of MAS825 on IL-6 is a 45% reduction (i.e., $\log(0.55)=0.60$, there is no effect on placebo, and the between subject SD of IL-6 is ≤ 0.5 using a 1 sided alpha of 10%.)

If MAS825 is not different from placebo, there will be a 10% chance of achieving the efficacy criteria (Type 1 error).

4 Change to protocol specified analyses

This SAP is based on the analyses described in the study protocol. Additional details and clarifications have been introduced to provide a more accurate description of the statistical plan.

5 Appendix

5.1 Imputation rules

5.1.1 Study drug

Not applicable.

5.1.2 AE date imputation

Table 5-1 Imputation of start dates (AE)

Missing Element	Rule
day, month, and year	
 • No imputation will be done for completely missing dates. AEs without a date won't be assigned to any treatment.
day, month	
 • If available year = year of study treatment start date then 
 • If stop date contains a full date and stop date is earlier than study treatment start date then set start date = 01JanYYYY • Else set start date = study treatment start date. • If available year > year of study treatment start date then 01JanYYYY • If available year < year of study treatment start date then 01JulYYYY
Day	
 • If available month and year = month and year of study treatment start date then 
 • If stop date contains a full date and stop date is earlier than study treatment start date then set start date= 01MONYYYY. • Else set start date = study treatment start date. • If available month and year > month and year of study treatment start date then 01MONYYYY

Missing Element	Rule
	
 If available month and year < month year of study treatment start date then 15MONYYYY

Table 5-2 Imputation of end dates (AE)

Missing Element	Rule (* = last treatment date plus 30 days not > (death date, cut-off date, withdrawal of consent date))
day, month, and year	
 Completely missing end dates (incl. ongoing events) will be imputed by the end date of the on-treatment period*
day, month	
 If partial end date contains year only, set end date = earliest of 31DecYYYY or end date of the on-treatment period *
Day	
 If partial end date contains month and year, set end date = earliest of last day of the month or end date of the on-treatment period*

Imputed dates may be used to classify an event as AEs/TEAEs within a treatment sequence, while they won't be used to assign any treatment in analyses by dosing session.

Any AEs and ConMeds with partial/missing dates will be displayed as such in the data listings.

Any AEs and ConMeds which are continuing as per data cut-off will be shown as 'ongoing' rather than the end date provided.

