2.1.1.2 Treatment sequence

In this study, participants are randomized to either of the five treatment sequences, each contains 4 dosing periods. The study treatment planned for each dosing period within each treatment sequence is shown below:

Treatment sequence 1: MAS825 – Placebo – Placebo – Placebo. Note that the effect of MAS825 is expected to persist over the entire 12-week treatment period. Therefore data collected in this sequence, after week 3 will be still assigned to MAS825.

Treatment sequence 2: Placebo – DFV890 10 mg – DFV890 25 mg – DFV890 100 mg

Treatment sequence 3: Placebo – DFV890 25 mg – DFV890 50 mg – DFV890 100 mg

Treatment sequence 4: DFV890 10 mg – DFV890 25 mg – DFV890 50 mg – DFV890 100 mg

Treatment sequence 5: Placebo – Placebo – Placebo – Placebo

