2.7.1 Adverse events (AEs)

Treatment-emergent AEs (TEAEs) are those with an onset after the start of a specific dosing period, or which were present prior to the start of the dosing period but increased in severity, changed from being not suspected to being suspected of study treatment relationship, or developed into SAEs after the start of the dosing period.

AEs with an onset outside the on-treatment period (before first dosing or more than 30 days from last dosing) will be just listed. AEs with a day of onset coinciding with the start of a new treatment will be assigned to the new treatment. Therefore AEs occurred on Day 1 will be considered TEAEs.

AE summaries will include all TEAEs occurred in the on-treatment period. All AEs collected in the AE CRF page will be listed by treatment sequence and participant, along with the information collected on those AEs e.g. AE relationship to study drug, AE outcome, etc.

AE summaries will be provided by treatment and by treatment sequence.

Summaries by treatment will be restricted to TEAEs occurred in the dosing periods (excluding TEAEs occurred in the follow-up) and percentages will be derived on the total number of dosing periods involved. This means that a participant treated with placebo for four 3-week treatment periods (as in treatment sequence 5) will be counted 4 times. Similarly, the same AE occurred in x separate dosing periods will be counted x times.

MAS825 dosing sessions will be defined as a 12-week interval from day 1 to Day 85 study visits.

Summaries by treatment sequence will consider all TEAEs occurred in the on-treatment period and will be referred to the number of participants assigned to each sequence.

An overview summary table will be provided reporting dosing sessions/participants with TEAEs (overall and by severity), treatment-related TEAEs (overall and by severity), serious TEAEs, and TEAEs/drug-related TEAEs leading to discontinuation of study treatment .

The number (and percentage) of dosing sessions/participants with TEAEs will be summarized by primary system organ class, and preferred term. An additional summary by primary system organ class, preferred term, and maximum severity will also be reported, as well as for serious (including fatal) TEAEs.

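### AEs with a partial or missing onset date drop out of the by-treatment AE summaries even when the participant could have been on only one treatment (SAP 5.1.2)

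*SAP*

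**What the plan says.** Table 5-1 in SAP 5.1.2 completes partial AE start dates by rule. The text after the tables allows these imputed dates to decide whether an event is treatment-emergent within a sequence, "while they won't be used to assign any treatment in analyses by dosing session". If no part of the start date is known, nothing is imputed and "AEs without a date won't be assigned to any treatment". The SAP states no other route from a partial date to a dosing session. It makes no exception for participants whose treatment label never changes.

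SAP 2.7.1 builds the by-treatment AE summaries on sessions, not people: "percentages will be derived on the total number of dosing periods involved". Events with onset in follow-up are left out of these summaries, and a MAS825 session is one 12-week interval. Several events in the same preferred term or system organ class count once per session. The by-sequence summaries are per participant and cover the whole on-treatment period.

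Two sequences carry a single treatment label. For Sequence 1, SAP 2.1.1.2 says: "Therefore data collected in this sequence, after week 3 will be still assigned to MAS825". Sequence 5 is placebo in all four periods.

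**The concern.** The rule works on one side of the fraction only. A session whose only event in a row has a partial date stays in the denominator and is shown as event-free. The stated rule can lower a by-treatment AE rate but cannot raise one.

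Safety and tolerability is a secondary objective, and Protocol 9.4.1 promises treatment-emergent AEs by treatment and dose. Participants in Sequences 2 to 4 pass through three or four DFV890 doses, so the by-sequence AE tables cannot attribute an event to a dose. Protocol 4.3 says that skin reactions cannot be excluded at 50 and 100 mg, and SAP 2.7.1.1 foresees possible rash analyses. Nothing asks for the number of unassigned AEs to be reported, so the by-sequence and by-treatment tables could disagree without explanation.

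In Sequences 1 and 5 an unknown day of onset cannot change which treatment was being taken. The SAP may accept such an event as treatment-emergent in the sequence column and still not place it under the only treatment that participant received.

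**Working it through.** **Inputs.** SAP Section 3 gives the numbers: "Twenty-eight (28) randomized participants in a 4:4:4:1:1 allocation to the treatment sequences will result in, approximately, 8 participants randomized" (in Sequences 1, 2 and 3 alike), and "2 participants to the third ascending dose sequence of DFV890 and to the placebo-only sequence". That is 28 × (4, 4, 4, 1, 1)/14 = 8, 8, 8, 2, 2. The sequences come from SAP 2.1.1.2:
- "Treatment sequence 2: Placebo – DFV890 10 mg – DFV890 25 mg – DFV890 100 mg"
- Sequence 3 starts on placebo and then runs 25, 50, 100 mg.
- Sequence 4 runs 10, 25, 50, 100 mg.
- Sequence 5 is placebo throughout.
- Sequence 1 counts as one MAS825 session per participant.

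**The plan's own figure.** Placebo sessions = 8 (Sequence 2) + 8 (Sequence 3) + 2 × 4 (Sequence 5) = 24. This matches the twenty-four placebo sessions in SAP 2.4.1, so the counting method agrees with the plan.

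**Largest effect of one lost event** = 100 / number of sessions.

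| Treatment | Sessions | Maximum loss (points) |
|---|---|---|
| Placebo | 8 + 8 + 8 = 24 | 4.2 |
| DFV890 10 mg | 8 + 2 = 10 | 10.0 |
| DFV890 25 mg | 8 + 8 + 2 = 18 | 5.6 |
| DFV890 50 mg | 8 + 2 = 10 | 10.0 |
| DFV890 100 mg | 8 + 8 + 2 = 18 | 5.6 |
| MAS825 | 8 | 12.5 |

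**Count-once rule.** If a share p of sessions already has a dated event in the row (p is an assumption; the documents give none), the expected loss is (1 − p) × 100 / sessions. At p = 0.5 this is 2.1 points on placebo, 2.8 on 25 and 100 mg, 5.0 on 10 and 50 mg, and 6.25 on MAS825.

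**Fewer sessions.** If 10% to 20% of sessions are not realised (also an assumption), the maxima rise to 4.6–5.2 (placebo), 6.2–6.9 (25 and 100 mg), 11.1–12.5 (10 and 50 mg) and 13.9–15.6 (MAS825).

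**How often the treatment is certain when only the day is missing.** Every Day 1 in one calendar year was crossed with 84 onset days, assuming exact 21-day periods. The day of the month was then hidden.

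| What is known | Sequences 1 and 5 | Sequences 2 to 4 |
|---|---|---|
| Onset known to lie in the dosing periods | 100% resolvable | about 18% |
| Pre-Day 1 and follow-up onset not ruled out | about 66% | 0% |

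The 0% is expected. A month has at least 28 days and a period 21, so a whole month always crosses a dose change in Sequences 2 to 4. Onset before Day 1 has to be considered because Protocol 8.6.1 collects AEs from informed consent.

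**The case against.** The strongest counter-argument is that the ban is right. Table 5-1 moves an on-treatment partial date to the earliest date it allows: the treatment start date, or the first of the month or year. Under ascending doses that would push events towards lower doses. Events in the month of Day 1 would land in period 1, which is placebo in Sequences 2, 3 and 5, and a DFV890 signal could be masked. This stands. It justifies not using the imputed date. It does not justify leaving out an event whose treatment is known without it.

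The events are also not hidden. Partially dated AEs can count in the by-sequence tables, and every AE is listed with its partial date as recorded. The Sequence 1 column has the same planned denominator of 8 as the MAS825 column, so an event missing from one can be seen in the other. Occurrence may be rare: Protocol 8.6.1 requires start and end dates and asks about AEs at each visit, and Protocol 10.1.5.2 has missing values queried. All of this stands and limits the weight of the point.

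A reader might infer four stronger things that the documents do not support:
- *All by-dose safety tables are affected.* Laboratory and vital-sign summaries are assigned by visit, not by AE onset (SAP 2.7.3, 2.7.4.2).
- *Each lost event costs 4 to 12.5 points.* These are ceilings because of the count-once rule. The two ends are placebo and MAS825; for DFV890 doses the ceiling is 5.6 to 10.
- *The dose-versus-placebo comparison is biased in a known direction.* Placebo loses events by the same rule, so the direction of any distortion is not established.
- *Wholly undated AEs are certain to be missing from the by-sequence tables.* The SAP says only that they get no treatment. It defines treatment emergence by onset and imputes nothing for them, which leaves their by-sequence status open.

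**Conclusion.** The point holds as a minor, avoidable undercount in the by-treatment AE summaries. For wholly undated AEs the exclusion is explicit. For partial dates it is inferred, because the SAP bars the imputed date and offers no alternative.

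The most one event can remove is 4.2 points (placebo), 5.6 (25 and 100 mg), 10 (10 and 50 mg) or 12.5 (MAS825). It removes nothing where the session already has a dated event in that row. These figures rest on the planned 8/8/8/2/2 allocation with every session realised. How many AEs will be affected is unknown and could be zero.

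The loss is needless mainly in Sequences 1 and 5, which hold 8 + 2 = 10 of the 28 planned participants, and there only once onset before Day 1 and in follow-up has been ruled out. In Sequences 2 to 4 a known month seldom settles the dose, so leaving those events unassigned in the main table is reasonable if their number is shown.

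**What to change.** Keep the ban on assigning treatment by the imputed date itself, and make three additions.

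1. In SAP 5.1.2: if every onset date compatible with the known date parts and the stop date falls in dosing periods carrying the same treatment, assign the AE to that treatment. With only the day missing, this recovers between about 66% (nothing further known) and 100% (onset known to be in the dosing periods) of such events in Sequences 1 and 5. In Sequences 2 to 4 it recovers between 0% and about 18%. For Sequence 5, also state which of the compatible placebo sessions carries the event, because the count-once rule works by session.
2. Under each by-treatment AE table: a footnote with the number of AEs not assigned to any treatment.
3. Assignment to the highest compatible dose only as a flagged worst-case sensitivity table. As a main rule it could create an artificial excess at 100 mg, and it would need to keep out events with possible follow-up onset.

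The cost is a few lines of SAP text and code. Trial conduct and data collection do not change.
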